8.2 Criteria for In-Study Decisions

Not applicable for this study.

8.3 Subject Withdrawal

If a subject wishes to leave the study at any time, they will be permitted to do so. Every reasonable effort will be made by Quotient Sciences to complete a final assessment/discharge procedures. Quotient Sciences will advise the sponsor of the withdrawal of any subject from the study.

Early withdrawal is defined as the date of the decision to withdraw the subject from the study. Subject completion is defined as the date of the last procedure conducted or last contact (ie phone call) for that subject.

If a subject requests to leave the clinical unit earlier than the planned discharge time eg due to unforeseen personal circumstances, but aims to return to the clinical unit to complete the study, this will be documented as a subject self-discharge and a protocol deviation. The subject must complete the planned assessments/discharge procedures before discharge from the clinical unit and will return for the next study period/assessments, as planned.

Subjects will be withdrawn from the study drug(s) for the following reasons:

- Experiencing a serious or severe AE including but not limited to:
 - corrected QT interval by Fridericia's formula (QTcF) of >500 msec or increase in QTcF interval of >60 msec from baseline (confirmed following a repeat ECG)
 - alanine aminotransferase (ALT) concentration >3 × the upper limit of the reference range (confirmed following a repeat ALT blood test)
- Experiencing a 25% decrease in creatinine clearance (CLcr)
- Termination of the study
- Upon the subject's request (withdrawal of consent)
- Significant deviation from the protocol
- Concurrent illness that would compromise subject safety of study data interpretation or requirement for prohibited medication
- At the discretion of the investigator

For the purpose of withdrawal criteria, baseline will be considered as pre-dose Day 1 measurement.

For a subject who withdraws because of an IMP-related AE, every effort will be made to ensure the subject completes follow-up procedures.

Early termination of the study will be distinguished from withdrawal of consent by the subject to participate in any further activities.

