5.3.2.1 Safety

Two large randomised, double blind, placebo-controlled Phase IIb-III studies have been conducted in patients with MS; 65 patients in study MS-ON for up to 6 months and 103 patients in study MS-SPI received 100 mg MD1003 TID for up to 12 months. Both studies have open label extension phases which are ongoing. The most commonly reported adverse events (>5% of patients) after treatment with MD1003 in these 2 completed randomised, double-blind, placebo-controlled studies, regardless of assessment of relationship to study treatment were nasopharyngitis, urinary tract infection, worsening of signs and symptoms of MS and MS relapse. The majority of reported adverse events were mild to moderate. Reported SAEs are consistent with the conduct of a trial in an MS patient population.

In completed studies with MD1003, a total of 4 serious adverse events (SAEs), reported in 4 patients and considered by investigators as being related to the study drug were reported. These SAEs included mucocutaneous rash, hypoglycaemia, transient myopathy and laboratory test interference.

In ongoing studies, one SAE (rash maculo-papular) in one patient with amyotrophic lateral sclerosis was considered as related to MD1003 by the investigator.

No deaths, SAEs, or AEs leading to treatment discontinuation with MD1003 were reported in the 4 healthy volunteer studies with MD1003 administered at doses up to 600 mg.

Based on MD1003 clinical and non-clinical data available, as well as the corpus of scientific and medical literature related to biotin, the following safety issues have been identified in patients treated with MD1003: interference with laboratory tests based on a biotin/streptavidin interaction, for which minimisation measures are in place (trial participation card and referral letter to general practitioner/hospital stating the subject has received a high biotin dose if a subject if withdrawn early), and a potential risk of teratogenicity observed in animal studies (rabbits). Since this study involves a single dose of biotin and subjects are planned to be discharged only after the administered dose has been eliminated, risk due to interference with laboratory results is considered

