to be very low and will be considered only if subjects are withdrawn early. In the case of early withdrawal, the risk minimisation measures above will be applied. In addition, some local allergic skin reactions have been observed. A single case of hypoglycaemia in an insulin-dependent patient and a single case of transient myopathy have also been reported in clinical trials. Adverse drug reactions reported in clinical trials to date are provided in [Table 2](#).

Table 2 Tabulated List of Adverse Reactions

| MedDRA System Organ Class | Adverse Reaction (Preferred Term) | Frequency Category |
|---|-----------------------------------|-----------------------|
| Metabolism and nutrition disorders | Hypoglycaemia ^a | Uncommon ^d |
| Skin and subcutaneous tissue disorders | Mucocutaneous rash ^b | Uncommon ^d |
| | Blister ^b | Uncommon ^d |
| | Eczema ^b | Uncommon ^d |
| Musculoskeletal and connective tissue disorders | Myopathy ^c | Uncommon ^d |

MedDRA: Medical Dictionary for Regulatory Activities

^a One patient (0.4%) with insulin-dependent diabetes experienced hypoglycaemic episodes, which occurred in the open-label phase of the studies approximately 1 year after initiation of MD1003. Episodes ceased when MD1003 was stopped and recurred on re-challenge.

^b During treatment with MD1003 in the double-blind placebo-controlled phases of the clinical studies, 1 (0.6%) patient developed a mucocutaneous rash, 1 (0.6%) patient cutaneous blisters and 1 (0.6%) patient eczema. No patients in the placebo group reported these events.

^c One (0.4%) patient developed transient myopathy, which occurred in the open-label phase of the studies 5 months after initiation of MD1003. The patient fully recovered when MD1003 was stopped.

^d Uncommon frequency category defined as $\geq 1/1000$ to $< 1/100$.

No serious adverse reactions have been listed as expected so far [\[1\]](#).

The safety profile of MD1003 is favourable, supporting the continuation of the clinical investigations program for the treatment of MS as planned.

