11.2 Administration of Test Preparations

Specific details of IMP(s) and doses to be administered are provided in [Section 5.2](#) and [Section 8.1](#), respectively. Subjects will be dosed on the morning of Day 1.

The exact time of dosing will be decided based on logistics and will be documented in the source.

Each subject will receive a single oral administration of a capsule containing 100 mg [¹⁴C]-MD1003 and NMT 2.22 MBq (60.0 µCi) on a single occasion in the fasted state.

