14.5.6 Abnormal Laboratory Findings

In cases where laboratory findings are outside the normal range and the investigator believes that the results may be of clinical significance, repeat sampling may be requested as clinically indicated. If the abnormal finding is clinically significant, appropriate actions will be taken eg the subject will not be entered into the study or the subject may be withdrawn from the study. The subject will be referred to their GP or other appropriate provider for further care. The same will apply if the results of the HBsAg, HCV Ab or HIV test are positive and in addition the investigator will ensure that adequate counselling is available if requested.

Abnormal results at follow-up assessments will also require repeat testing if the investigator believes the results may be of clinical significance.

Any clinically significant abnormality, including changes from baseline, must be reported as an AE.

Additional blood and/or urine samples may be taken for safety tests. Furthermore, additional assays outside those specified in the protocol may be performed for safety reasons as requested by the investigator or sub-investigator.

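### Does withdrawing a subject from study drug after the only dose put the mass balance endpoint at risk?

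*Protocol*

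**What the plan says.** Protocol 8.3 opens its list with "Subjects will be withdrawn from the study drug(s) for the following reasons". The list covers serious or severe adverse events (with QTcF and ALT limits as examples), a fall in creatinine clearance ("Experiencing a 25% decrease in creatinine clearance (CLcr")), study termination, withdrawal of consent, protocol deviation, concurrent illness and investigator discretion. It then fixes the reference value: "For the purpose of withdrawal criteria, baseline will be considered as pre-dose Day 1 measurement". The same section also states: "Early withdrawal is defined as the date of the decision to withdraw the subject from the study".

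Three other places bear on this:

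- 11.2 gives the capsule "on a single occasion in the fasted state".
- 14.5.6 says of a clinically significant laboratory abnormality that, as one possible action, "the subject may be withdrawn from the study".
- 5.3.2.1, on biotin interference with laboratory tests, says "subjects are planned to be discharged only after the administered dose has been eliminated", and adds "In the case of early withdrawal, the risk minimisation measures above will be applied".

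On creatinine clearance itself, 14.5.1, the Appendix 1 footnote and Appendix 2 note c describe a Cockcroft-Gault calculation at screening, for eligibility.

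**The concern.** With one dose and a baseline taken before it, a 25% fall can be seen only after the capsule has been swallowed. A mandatory withdrawal from study drug then has nothing to act on. A reader looks for another meaning and finds one: 8.3 dates early withdrawal from a decision about the study, 14.5.6 speaks of the study, and 5.3.2.1 sets early withdrawal against planned discharge after elimination. On that reading a triggered subject might leave while radioactivity is still being excreted.

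The stake would be real. Cumulative percentage recovery is a primary endpoint, and no analysis rule can restore excreta that were never collected. Only six subjects are enrolled, none is replaced, and four must be evaluable. The screening-only text on creatinine clearance adds to the unease, because 8.3 needs a Day 1 value and a later one.

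**Working it through.** The protocol makes no formal sample size calculation (15.1), so there is no figure to reproduce. The check compares the sections and then asks how large the effect could be.

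**1. What happens to collection under each reading**

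| Reading of 8.3 | What the protocol then provides | Effect on collection |
|---|---|---|
| Withdrawn from drug (literal) | 8.1 and 10.3.3 stop sampling when the release criteria or the planned residency have been reached; neither names an 8.3 trigger | None |
| Withdrawn from the study | Precautions for early withdrawal (5.3.2.1), evaluability rule (8.4), handling of withdrawn subjects' data left to the Reporting and Analysis Plan (15.6) | May stop early; not stated |

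No section says that collection stops, or continues, after a trigger. The protocol is silent here and does not contradict itself. The passage in 5.3.2.1 concerns laboratory interference and shows only that early withdrawal can occur. The discretionary wording in 14.5.6 is a general example for any abnormal result, and it can stand beside specific mandatory items in 8.3.

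**2. Whether the trigger can be computed**

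From the 14.5.1 formula, CLcr = (140 − age) × weight × 1.23 / creatinine. At fixed age and weight, CLcr is proportional to 1/creatinine, so a 25% fall means a creatinine rise of 1/0.75 − 1 = 33.3%. Creatinine is in the Appendix 1 panel, Appendix 2 note c has clinical chemistry at each laboratory time point, and 14.5.1 gives windows for pre-dose and post-dose safety samples. The inputs therefore appear to be collected, although the Appendix 2 grid is not shown.

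**3. How much collection could be lost**

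From Appendix 2 notes e and f, urine intervals to 168 h are 0–12 h, 12–24 h and six daily ones, 8 in all. Faecal intervals are 7.

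| Assumed time of leaving | Urine kept | Faeces kept | 72 h condition in 8.4 |
|---|---|---|---|
| 24 h | 2 of 8 | 1 of 7 | not met |
| 48 h | 3 of 8 | 2 of 7 | not met |
| 72 h | 4 of 8 | 3 of 7 | met |

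Even at 24 or 48 h the subject stays evaluable if a recovery criterion in 8.4 has already been met. These times are assumptions; the visible text gives no post-dose chemistry time.

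**4. Illustrative shortfall in recovery**

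Section 5.3.1 gives oral bioavailability of about 50%. Assume that the unabsorbed half leaves in faeces and that urinary recovery is already complete when the subject leaves. Then shortfall = 50 × (1 − share of that half already passed):

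- share 0: 50 points, which lowers a six-subject mean by 50/6 = 8.3 points
- share 0.5: 25 points, mean lower by 25/6 = 4.2 points
- share 1: 0 points

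The second assumption is favourable; incomplete urinary recovery would add to the loss. The result follows the assumptions and reaches zero within their range.

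**5. Whether four evaluable subjects are at risk**

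The margin is 6 − 4 = 2 losses. With an assumed probability p that a subject is not evaluable for any reason, independent between subjects, P(at least 4 of 6) = Σ C(6,k) p^k (1−p)^(6−k) for k = 0 to 2.

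- p = 0.05: 0.998
- p = 0.10: 0.531 + 0.354 + 0.098 = 0.984
- p = 0.20: 0.901

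The creatinine trigger would be only one contributor to p.

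**The case for a change.** The strongest case for acting is that whether a subject stays for collection is a matter of conduct, so it belongs in the protocol; an analysis plan cannot repair it afterwards. The list in 8.3 contains study-level events such as consent withdrawal and termination, so staff could fairly read every item as leaving the study. The sentence asking for follow-up procedures covers only withdrawal for an IMP-related adverse event and does not mention excreta. The creatinine item also lacks the repeat confirmation attached to QTcF and ALT.

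Parts of this stand. The drug wording is empty after a single dose, the section moves between drug and study, and the creatinine clearance text stops at screening. The wording problem is not specific to creatinine, however: it applies equally to the post-dose QTcF and ALT items, which suggests template language carried over from multiple-dose studies.

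The step from loose wording to lost endpoint data does not stand. It needs a trigger of unstated frequency in men admitted with clearance of at least 80 mL/min (9.3). Section 5.3.1 reports no untoward renal effect in animals, and 5.3.2.1 reports no adverse events leading to discontinuation in the four healthy volunteer studies. It also needs detection before 72 h, no recovery criterion met, and a decision to send the subject home that no section requires. Physician review of results (14.5), adverse event reporting (14.5.6) and investigator discretion (8.3) remain in place, so no safety gap arises.

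**Conclusion.** The concern does not call for a change. Following 8.3 as written leaves a triggered subject in collection with a sound recovery figure. Following it as withdrawal from the study gives an ordinary early withdrawal, for which the protocol already has an evaluability rule, a margin of two subjects and a place for data handling. The mixed use of drug and study is a clerical slip. The missing mention of creatinine clearance after screening is a detail that staff can fill from creatinine values that appear to be collected anyway.

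No effect on the primary endpoint can be quantified from the protocol. The mean shortfalls of 8.3, 4.2 or 0 points rest on one subject leaving early, on the assumed split of the dose and on complete urinary recovery. The probability of 0.984 rests on an assumed 10% loss per subject. The conclusion would weaken only if early triggers were frequent and the site treated each one as discharge, and nothing in the protocol points to either. The wording can be tidied if the protocol is amended for another reason; what the clinical rule should be is outside this review.

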8.4 Subject Replacement

No replacement subjects are to be used in this study.

A subject will be considered evaluable if they have provided mass balance and PK samples for up to 72 h (up to Day 4) after IMP administration, or have demonstrated >90% mass balance recovery, or have <1% of the administered dose eliminated in excreta for 2 consecutive days, whichever is sooner.

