Subjects will be dosed on the morning of Day 1 following an overnight fast and will remain resident in the clinical unit until up to 168 h after dosing (up to Day 8). It is planned that subjects will be released as a group when all subjects have achieved a mass balance cumulative recovery of >90% or if <1% of the dose administered has been collected in urine and faeces within 2 separate consecutive 24 h periods. This may result in the subjects being discharged as a group prior to completion of the planned residency period. Once the discharge criteria or the planned residency period have been achieved, collection of all samples (blood, urine and faeces) will be stopped and the subjects will undergo discharge assessments. If the mass balance criteria have not been met by all subjects by Day 8, the residency period for the subjects not achieving the release criteria may be extended up to a maximum of an additional 48 h (up to Day 10) for further collection of urine and/or faeces. If the release criteria have still not been met by Day 10, or if any additional residency is not considered appropriate or necessary, then home collections of urine and/or faeces may be requested at the discretion of the investigator for individual subjects.

Number of Subjects Planned:

It is planned to enrol 6 healthy male subjects to ensure data in 4 evaluable subjects. A subject will be considered evaluable if they have provided mass balance and PK samples for up to 72 h (up to Day 4) after IMP administration, or have demonstrated >90% mass balance recovery, or have <1% of the administered dose eliminated in excreta for 2 consecutive days, whichever is sooner. No replacement subjects are to be used in this study.

Duration of Study:

Single oral dose administration on a single occasion. The estimated time from screening until the end of the study is approximately up to 6 weeks.

Main Inclusion Criteria:

Healthy males aged 30 to 65 years.
 Body mass index (BMI) 18.0 to 30.0 kg/ m².

Investigational Medicinal Product, Dose and Mode of Administration:

The following IMP will be used in this clinical study.

| Treatment | IMP Name | Dose | Route of Administration |
|-------------|-----------------------------------|--|-------------------------|
| Single dose | [¹⁴ C]-MD1003 Capsule | 100 mg (NMT 2.22 MBq; 60.0 µCi ¹⁴ C) | Oral, fasted |

¹⁴C: carbon 14, NMT: not more than

All doses will be administered orally with 240 mL water, following an overnight fast.

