5.3.1 Non-clinical Findings

The hypothesised positive effects of MD1003 that may be seen in demyelinating or dysmyelinating diseases such as MS are thought to be linked to: (1) increased energy production through augmenting the TCA cycle in demyelinated neurons, and (2) stimulation of myelin repair through activation of the acetyl-CoA carboxylase in oligodendrocytes.

Following oral administration, biotin is absorbed in the intestine via the sodium multivitamin transporter (SMVT). At the therapeutic dose level, biotin has good oral bioavailability (~50%) and is largely not bound to plasma proteins. Following an oral administration of MD1003 in rats, the highest concentrations were found in the stomach, bladder, and kidneys with a rapid elimination with very low concentrations after 24 h and no storage of biotin observed. Biotin uptake into the CNS, liver, and most peripheral tissues also involves the SMVT. No saturation of the SMVT at the blood-brain barrier is expected at the therapeutic dose. Biotin may accumulate in the placenta and is excreted in milk in animals. Biotin is catabolized mostly in the liver via 2 pathways leading to 2 main metabolites, bisnorbiotin and biotin sulfoxide. Biotin metabolites are inactive. Following an intravenous administration of MD1003 in rats, biotin and its metabolites are rapidly excreted in the urine (>80% of elimination) with biotin being the major form excreted. Urinary clearance data obtained following administration of MD1003 in healthy volunteers suggest that biotin is actively secreted by the kidneys.

Drug interaction with MD1003 treatment involving cytochrome P450 enzymes or transporters commonly involved in the absorption, metabolism and elimination of other drugs are not expected. The expected risk of drug interaction with MD1003 administration in humans resides mainly from pharmacodynamic interaction with insulin and pharmacokinetic (PK) interactions with other substrates of the biotin transporter (SMVT) and some antiepileptic drugs (carbamazepine, oxcarbazepine, primidone, and valproate semisodium).

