5.3.4 Pharmacokinetics and Product Metabolism in Animals

Full details of PK and absorption, metabolism, distribution and elimination (ADME) data can be found in the Investigator's Brochure [1].

In the GLP Study MD1003-ADME-RAT, the radioactivity was rapidly eliminated from plasma after intravenous administration of 10 mg/kg ¹⁴C-MD1003. After oral administration of 30 mg/kg ¹⁴C-MD1003 (human equivalent therapeutic dose), the radioactivity was rapidly absorbed and after a first phase of rapid elimination from the plasma, the radioactivity was then slowly eliminated.

At physiological doses of [¹⁴C] biotin (88 nmol/kg body weight) given orally to pigs, the plasma concentration profile best fitted a tri-exponential equation [9], which corresponds to a tricompartamental open model. Disappearance curves of total ¹⁴C and of [¹⁴C] biotin were similar. Biotin pharmacokinetics after intravenous injection of [¹⁴C] biotin was marked by a very short half-life of the initial distribution phase (7 min), followed by a slower plasma elimination phase (T_{1/2}, β of 1.43 h) and a long apparent terminal half-life T_{1/2}, γ estimated at 22 h. The rapid initial distribution phase was shown to correspond to the disappearance of biotin from the plasma (central compartment) to the peripheral compartments, such as the total body water pool or tissue pools [9].

The retention over many days of a substantial portion of the administered dose may occur as a consequence of the metabolic trapping of biotin into cells: conversion of biotin to intermediates such as biotinyl-adenosine monophosphate and biotinyl-CoA, or binding of biotin to proteins such as carboxylases and histones [9]. The half-life of pyruvate carboxylase was determined to be 28 h and 4.6 days for acetyl-CoA carboxylase [10].

Overall, PK data obtained with MD1003 confirmed the literature data and completed the PK properties of biotin:

- Biotin is rapidly absorbed by the oral route in animals

- At the equivalent therapeutic dose in rats (30 mg/kg), biotin is not completely absorbed
- At very high doses (up to 3000 mg/kg), plasma exposure does not significantly increase, suggesting that the transport is saturated
- The major route of elimination is urinary and most of the biotin is excreted unchanged
- There was no evidence of accumulation after once daily repeated dosing in animals

6 Rationale

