8.1 Study Plan

[figure not shown]
This is a single-centre, open-label, non-randomised, single oral dose study in healthy male subjects. It is planned to enrol 6 subjects to ensure 4 evaluable subjects.

Each subject will receive a single oral administration of a capsule containing 100 mg MD1003 and NMT 2.22 MBq (approximately 60.0 µCi) [¹⁴C], in the fasted state.

The study design is presented in [Figure 1](#). Subjects will be screened to participate in the study up to 28 days before dosing. Subjects will be admitted to the clinical unit on the evening of Day -1 prior to IMP administration.

Subjects will be dosed on the morning of Day 1 following an overnight fast and will remain resident in the clinical unit until up to 168 h after dosing (up to Day 8). It is planned that subjects will be released as a group when all subjects have achieved a mass balance cumulative recovery of >90% or if <1% of the dose administered has been collected in urine and faeces within 2 separate consecutive 24 h periods. This may result in the subjects being discharged as a group prior to completion of the planned residency period. Once the discharge criteria or the planned residency period has been achieved, collection of all samples (blood, urine and faeces) will be stopped and the subjects will undergo discharge assessments. If the mass balance criteria have not been met by all subjects by Day 8, the residency period for the subjects not achieving the release criteria may be extended up to a maximum of an additional 48 h (up to Day 10) for further collection of urine and/or faeces. If the release criteria have still not been met by Day 10, or if any additional residency is not considered appropriate or necessary, then home collections of urine and/or faeces may be requested at the discretion of the investigator for individual subjects.

Figure 1 Study Sequence

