15.1 Sample Size Justification

The study is exploratory and no formal sample size calculation has been made. Based on experience from previous studies of a similar design, a total of 6 subjects is to be enrolled and a minimum of 4 evaluable subjects is considered sufficient.

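### Does the definition of an evaluable subject in sections 3 and 8.4, which 72 h of samples satisfies at any recovery, undermine the planned minimum of 4?

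*Protocol*

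**What the plan says.** The protocol's section 8.4 opens its definition with "A subject will be considered evaluable if they have provided mass balance and PK samples for up to 72 h (up to Day 4"), adds recovery above 90% as an alternative, and ends "or have <1% of the administered dose eliminated in excreta for 2 consecutive days, whichever is sooner". The synopsis (section 3) repeats this and gives its purpose: "It is planned to enrol 6 healthy male subjects to ensure data in 4 evaluable subjects". Section 15.1 states that no formal sample size calculation was made and that "a minimum of 4 evaluable subjects is considered sufficient". Section 8.4 allows no replacements.

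Section 8.1 sets how long excreta are collected. Subjects "will remain resident in the clinical unit until up to 168 h after dosing (up to Day 8"), with earlier release as a group once all have recovery above 90% "or if <1% of the dose administered has been collected in urine and faeces within 2 separate consecutive 24 h periods". Subjects who have not met these criteria by Day 8 may stay until Day 10, and home collection may follow.

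On how fast the dose leaves the body, the background sections point both ways. Section 5.3.4 says, after pig data at physiological doses, that "The retention over many days of a substantial portion of the administered dose may occur". Section 5.3.1 reports for rats "rapid elimination with very low concentrations after 24 h and no storage of biotin observed".

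**The concern.** The three conditions are joined by *or*, so the two that concern recovery can only add subjects to the count and never remove one. Samples to 72 h are enough at any recovery, and the phrase used for 72 h literally sets an upper limit rather than a lower one. For a subject who already has 72 h of samples, the low-excretion condition does nothing.

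Section 8.1 uses the same two recovery criteria with a 168 h horizon, where they do real work. No reason is given for 72 h.

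The minimum of 4 is the protocol's only statement of adequate size, and mass balance is a primary objective. As worded, the minimum could be declared met with no excreta data beyond 72 h. If part of the dose were retained for days, 4 evaluable subjects would then not mean 4 subjects with near-complete recovery.

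**Working it through.** **No figure to reproduce.** Section 15.1 reports no formal calculation. The only arithmetic is 6 − 4 = 2 tolerated losses.

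**Logic.** Let A = samples to 72 h, B = recovery above 90%, C = below 1% on two consecutive days. Section 8.4 is A or B or C; the section 8.1 early-release criteria are B or C. Of the eight combinations, the two rules differ in exactly one: A true, B and C false. That subject is evaluable under 8.4 but not releasable on recovery under 8.1. The two rules answer different questions, so this is a difference in stringency and not a contradiction.

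**What the recovery conditions are for.** Section 8.1 lets the group leave early on B or C, after which all sampling stops. Repeating B and C in 8.4 keeps a subject released before 72 h in the count.

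**When C can act.** Pairs of 24 h periods end at 48 h, 72 h, 96 h and so on. To be met before 72 h, both 0–24 h and 24–48 h must be below 1%, which means under 2% of the dose by 48 h. For a subject with complete samples, C is therefore idle. But A requires PK samples as well as excreta. A subject with complete excreta and incomplete PK samples, whose recovery levels off below 90%, counts only through C, which he may meet after 72 h. So C is not redundant.

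**Chance that the count misleads.** For the count to be at least 4 with fewer than 4 followed to the 8.1 end point, at most 3 are followed, so at least 3 of 6 stop early. With independent early stopping at an assumed probability p, P(X ≥ 3) for X ~ Binomial(6, p) is:

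| p (assumed) | P(X ≥ 3) |
|---|---|
| 0.05 | 0.0022 |
| 0.10 | 0.0159 |
| 0.20 | 0.0989 |

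These are upper bounds, because at least one of those who stop must also have reached 72 h.

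**Recovery at 72 h and 168 h.** Take recovery(t) = 100 − s·2^(−t/h), where s is an assumed slowly excreted share (% of dose) and h a half-life from section 5.3.4.

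| h | s | 72 h | 168 h |
|---|---|---|---|
| 22 h | 50 | 94.8 | 99.7 |
| 28 h | 50 | 91.6 | 99.2 |
| 110.4 h (4.6 days) | 15.7 | 90.0 | 94.5 |
| 110.4 h (4.6 days) | 50 | 68.2 | 82.6 |

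At 22 h or 28 h, even a 50% slow share meets the 90% criterion by 72 h, so the 72 h condition adds nobody. Only the 4.6-day value, with a slow share above about 15.7% (10 / 0.636), leaves recovery short of 90% at 72 h. That value is an enzyme half-life (acetyl-CoA carboxylase), not a measured excretion half-life.

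In that slowest case, one subject of six stopping at 72 h rather than 168 h would lower mean cumulative recovery by 4.53/6 = 0.75 to 14.40/6 = 2.40 points. That loss comes from stopping early. The subject contributes the same data whether or not he is called evaluable.

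**What the count drives.** Section 8.2 has no in-study decisions, 8.4 no replacements and 15.6 no formal tests. Section 15.6 leaves the analysis sets and the handling of withdrawn subjects to the Reporting and Analysis Plan, and all mass balance data are listed.

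**The case for a change.** The strongest case for a change is that the minimum of 4 is all the protocol offers on adequacy, that it can be satisfied without any information on late excretion, and that one sentence would repair it. Section 5.3.4 supports the worry: besides the retention statement, it reports slow later elimination of radioactivity from plasma in rats after oral dosing. Section 5.3.2.1 assumes that subjects leave only once the dose has been eliminated.

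The logical reading stands, and so does the remark on wording. The rest does not lead to a better plan.

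- **Keep 72 h as an explicit minimum and delete the low-excretion condition.** This is not neutral, because it drops the subject with complete excreta but incomplete PK samples described above. It also leaves a condition based on time alone.
- **Tie the count to the section 8.1 criteria.** A time-only condition remains, now at 168 h. At 4.6 days and a 50% slow share, recovery at 168 h is 82.6% with 2.83% of the dose excreted in 144–168 h, so neither recovery criterion is met and time alone decides. The count could also fall below 4 with no replacements allowed.

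Choosing between 72 h and 168 h as the floor is a trade-off for the sponsor. Section 5.3.4 also ends with no evidence of accumulation on repeated daily dosing in animals and mainly urinary excretion of unchanged biotin, which weakens the case for a long retained fraction.

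**Conclusion.** No change to the plan follows. A subject with 72 h of mass balance and PK samples does count as evaluable at any recovery, but this does not conflict with section 8.1, which keeps all six under collection to 168 h or beyond unless the recovery criteria are met. Only the headcount of 4 is affected. The chance that it overstates follow-up is at most 0.2% to 9.9% for assumed early-stopping probabilities of 5% to 20%, and it matters only if excretion is as slow as the 4.6-day enzyme half-life with a slow share above about 15.7%.

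Describing 72 h as an upper limit is a clerical slip. Section 8.1 writes its residency period in the same style, and any analyst will read the condition as samples through 72 h.

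This rests on the protocol alone. The Reporting and Analysis Plan was not available; if it reused the section 8.4 wording for its mass balance set the effect would be wider, but nothing in the protocol says that it does.
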